### 3.3.12.4 Aim 3 (To test whether or not characteristics of the drug administration session experiences mediate effects of psilocybin on short term (1 week) persisting effects and post-session drinking behavior).

#### 3.3.12.4.1 Measures

The three main dimensions of the 5D-ASC ("oceanic boundlessness," "anxious ego-disintegration," "visionary restructuralization,") and the total score from the MEQ will be used as independent measures of acute drug effects. Short term (1-week post-session) effects will be the as follows: for craving, the primary measure is the total score from The Penn Alcohol Craving Scale [148]; for self-efficacy, Abstinence Confidence from the Alcohol Abstinence Self-efficacy Scale [143]); and for motivation the "readiness" score from the Readiness Rulers [142]. Drinking outcomes will be those specified for Specific Aim 2.

#### 3.3.12.4.2 Method

Tests of statistical mediation will use a product-of-coefficients approach with a bootstrapping procedure. This choice provides the most powerful test of mediation with smaller samples and does not assume normality in the distribution of ( $a'b'$ ) product terms (Preacher and Hayes, 2008; Hayes, 2009). HLM will be applied to identify the  $a$  and  $b$  parameter estimates for the between-group contrast (treatment assignment psilocybin versus control;  $df = 1$ ), and baseline values of the dependent variable will be entered in level 2.

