
**Aim 1:** To characterize the acute effects of PO psilocybin 25 mg/70 kg, 30 mg/70 kg, and 40 mg/70 kg in alcohol dependent patients: Hypothesis 1: The drug will be well-tolerated, and acute effects will be similar to those observed in normal volunteers.

**Aim 2:** To evaluate the effect of psilocybin treatment on drinking outcomes for 32 weeks after the first administration, relative to diphenhydramine control. Hypothesis 2: A greater decrease in percent heavy drinking days will be observed among participants receiving psychoactive doses of psilocybin in combination with psychosocial treatment than in those receiving diphenhydramine.

**Aim 3:** To test whether or not characteristics of the drug administration session experiences mediate effects of psilocybin on short term (1 week) persisting effects and post-session drinking behavior. Hypothesis 3: Intensity of experience during the drug administration sessions will predict post-session changes in craving, self-efficacy, and motivation, and these changes will in turn predict changes in drinking behavior during the 32 weeks following initial drug administration.

**Aim 4:** To evaluate the explanatory value of changes in alcohol craving, self-efficacy, motivation, and other psychological domains in accounting for the observed experimental effect of psilocybin relative to diphenhydramine control. Hypothesis 4: Changes in craving, self-efficacy, and motivation will mediate the effects of psilocybin treatment on drinking behavior.

**Aim 5:** To evaluate pre-post changes in drinking in participants after they receive psilocybin in the third session. Hypothesis 5: participants in the control group will show decreases in drinking during the 16 weeks following the psilocybin session at week 38.

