### **3.3.10.8 Potential Moderators of Acute and Persistent Effects of Psilocybin**

In addition to the participant characteristics measured above, the following measures will be obtained at baseline.

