#### ***3.3.10.8.2 Thoughts About Abstinence***

Using the form that was used in the COMBINE trial [156], participants will be asked to endorse one of seven treatment goals which can be categorized as: 1) total abstinence; 2) conditional abstinence; and 3) moderation.

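### Aim 3 mediation test: the link from session experience to outcome is not randomised and is adjusted, in the protocol, only for the baseline outcome, so a shared baseline trait could pass as mediation

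*Combined protocol and SAP*

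**What the plan says.** Section 2 words Aim 3 causally: "To test whether or not characteristics of the drug administration session experiences mediate effects of psilocybin on short term (1 week) persisting effects", and on drinking after the session. Section 3.3.12.4.1 names three 5D-ASC dimensions and the MEQ total, which "will be used as independent measures of acute drug effects". The outcomes are one-week craving, self-efficacy and readiness, and for drinking: "Drinking outcomes will be those specified for Specific Aim 2".

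The method in 3.3.12.4.2 is: "Tests of statistical mediation will use a product-of-coefficients approach with a bootstrapping procedure". Hierarchical models supply the a and b "parameter estimates for the between-group contrast (treatment assignment psilocybin versus control", and "baseline values of the dependent variable will be entered in level 2". No other covariate is named. The section states no assumption about confounding between mediator and outcome, and no sensitivity analysis.

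Other sections collect participant traits before dosing. Section 3.3.10.8, headed "Potential Moderators of Acute and Persistent Effects of Psilocybin", lists the ARAS (absorption and dissociation) and a goal form on which "participants will be asked to endorse one of seven treatment goals", grouped into three categories. Section 3.3.10.6.2 adds the NEO-PI-3 at baseline. Section 3.1.8.1 says that the effects of these drugs are expected to depend strongly on the person and the setting.

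**The concern.** Participants are randomised to a drug, not to a stronger or weaker session. Within an arm, how intense the session is may depend on who the participant is. Someone more absorbed, more open or more committed to abstinence might have a stronger session and also drink less afterwards. If so, path b is non-zero even when the experience has no effect, and the product a × b is non-zero with it.

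The analysis would then credit the session experience with a benefit that belongs to the trait. Aim 3 is a named aim with its own hypothesis, and section 3.2 presents the study of change mechanisms as one of the trial's innovations, so such an error would misstate a headline secondary result.

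**Working it through.** **Plan's own figures.** The protocol gives no power or error rate for Aim 3; the only power figure (3.3.12.7) concerns Aim 2, and nothing here rests on it. That section supplies N = 0.95 × 180 = 171, or 85.5 per arm. The pilot correlation of MEQ with change in heavy drinking (Figure 3d, r = −.823, n = 9) reproduces: t = −.823 × √(7 / (1 − .823²)) = −3.83 on 7 df, p = .0064, against the stated .006. All nine received psilocybin, so a within-arm association is plausible. It cannot show whether the experience or a trait lies behind it.

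**Step 1: path a.** The documents give no arm difference or SD for the session scores. For an assumed standardised difference d, the noncentrality is d × √(85.5/2) = 6.54d. Power for path a is 0.905 at d = 0.5, 0.999 at d = 0.8 and 1.000 at d of 1 or more. In simulations with a = 1 or 2 SD, the rejection rate for a × b matched that for b alone to within 0.001. The mediation test is then a test of b.

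**Step 2: what a shared trait does to b.** Suppose a trait has within-arm correlation r with the session score and partial correlation r with the outcome, given the baseline outcome. With the true effect of the score set to 0, the induced within-arm partial correlation is ρ = r². The test of b has noncentrality ρ/√(1 − ρ²) × √171 on 171 − 4 = 167 df (critical t = 1.974).

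**Step 3: simulation.** Percentile bootstrap of a × b, a = 2 SD, baseline-outcome coefficient 0.5, true b = 0, 171 or 180 participants. The runs at 90 per arm used 600 trials and 400 resamples; simulation error is about 1–2 points. The score SD was 1 under psilocybin and 0.3 under control, which shrinks the pooled ρ by a factor of .65/√.545 = 0.88.

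| Trait r (both links) | ρ = r² | Noncentrality | Rejection, formula, equal SDs | Rejection, simulated, control SD 0.3 |
|---|---|---|---|---|
| 0 | 0 | 0 | 5% | 4–7% |
| .2 | .04 | 0.52 | 8% | 7–10% |
| .3 | .09 | 1.18 | 22% | 19–22% |
| .4 | .16 | 2.12 | 56% | 46–53% |
| .5 | .25 | 3.38 | 92% | 83–87% |

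The last column spans repeated runs. With one link absent the rate stays nominal: 5% with only a session link of .3, and 4% with only a drinking link of .5.

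**Step 4: size of the false effect.** In a second set-up the trait correlates .5 with the score and has a standardised coefficient of −.5 on drinking. There ρ = −.25/√.75 = −.29. The spurious indirect effect averages −0.25 SD at a = 1 and −0.50 SD at a = 2, so it grows with path a although b is truly zero. At a = 2 the false-mediation rate is 96%, and 98% if the drug works wholly by another route.

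**Step 5: after adjustment.** In the Step 3 design, entering the trait in both models brings the rate to about 4–8% if it is measured without error, and about 5–16% at reliability 0.8. In the Step 4 set-up with a = 2, the rates are 7% without error and 32% at reliability 0.7.

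**The case against.** The strongest reply is that this is the ordinary no-confounding assumption of any mediation analysis with an unrandomised mediator. That is correct. A reader might infer that the bootstrap, the product of coefficients or the large path a is at fault. None is: with a non-zero, a × b = 0 exactly when b = 0. The defect is what the protocol leaves out around path b.

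A reader might also infer that any within-arm correlation would trigger a false finding. The table does not support this: at r of .2 or less the inflation is a few points, and the high rates need .4 to .5 on both links after baseline drinking has been removed.

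Nor do the documents show that any named trait is a confounder. ARAS and treatment goal are listed as potential moderators, a different role. The NEO-PI-3 is included because psilocybin may change openness. No section gives any of them a link to both session response and drinking. This stands, and it is why the correlations are presented as assumptions.

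The existing adjustment may also do more than the simulation credits. If the Aim 3 baseline is the week 1–4 heavy-drinking value used in 3.3.12.3.2, which falls after therapy starts, it would already absorb part of a participant's commitment to change. The simulated trait is independent of baseline drinking. Section 3.3.12.4.2 does not say which baseline is meant.

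Finally, Hypothesis 3 speaks of prediction and the method of statistical mediation, which is softer than the aim. But the aim itself uses the causal word, and nothing in the section limits how a positive result would be described.

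**Conclusion.** The point holds as a limited one. Followed as written, 3.3.12.4.2 can attribute to the session experience an association that comes from a baseline trait, because path b is unrandomised and only the baseline outcome is adjusted for. The false-mediation rate is close to nominal at trait correlations of .2 or less, about 20% at .3, about 50% at .4 and about 85% at .5.

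These sizes rest on assumed trait correlations, an assumed 2 SD path a, a single summary outcome and a trait unrelated to baseline drinking. Repeated measures in the hierarchical model would not remove person-level confounding.

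It would go too far to call a large path a certain. Section 3.3.8.1.2 describes a powerful subjective effect, but section 3.3.3.2 reports pilot effects weaker on average than in normal volunteers, with MEQ from .02 to .77. Very likely is the supportable wording, and the argument needs only d of about 0.8.

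It would also go too far to say that the trial has no such adjustment. Section 3.3.12 refers to a separate SAP for the full analyses, and its text is not in the document reviewed. What can be said is that the protocol names none. The primary Aim 2 comparison is untouched.

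**What to change.** In 3.3.12.4.2:

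- Enter the baseline ARAS score, treatment-goal category and NEO-PI-3 openness in both the mediator model and the outcome model, alongside the baseline value of the outcome. State which baseline period that is.
- Add a sensitivity analysis reporting the residual mediator–outcome correlation that would reduce the indirect effect to zero. The r² rule above helps to read it: a residual correlation of .09 is what a single trait at .3 on both links would produce.
- State that the result will be described as mediation only under no remaining confounding between session experience and outcome, and otherwise as an association.

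The cost is 1 + 2 + 1 = 4 degrees of freedom (ARAS, three goal categories, openness), some lines of code and a more cautious claim. No new data are needed, and fixing the covariates in advance prevents choosing them after the results are known. The three traits are a reasonable choice from what is collected, not a set that the documents show to be sufficient, and measurement error will leave some confounding. For that reason the sensitivity analysis and the conditional wording matter most. Section 3.3.12.5.2 borrows the same procedure for Aim 4, so the sponsor should say whether the change carries over. If the separate SAP already contains these elements, only 3.3.12.4.2 needs to be brought into line.

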## 1. PROTOCOL ABSTRACT

Several lines of evidence suggest that classic hallucinogens such as psilocybin can facilitate behavior change in addictions such as alcohol dependence. The proposed investigation is a multi-site, double-blind active-controlled trial (n = 180, 90 per group) contrasting the acute and persisting effects of psilocybin to those of diphenhydramine in the context of outpatient alcoholism treatment. Two to four sites will participate. Aims of the study are 1) to characterize the acute effects of PO psilocybin 25 mg/70 kg, 30 mg/70 kg, and 40 mg/70 kg in alcohol dependent patients; 2) to evaluate the effect of psilocybin treatment on drinking outcomes for 32 weeks after the first administration, relative to diphenhydramine control; 3) to test whether or not characteristics of the drug administration session experiences mediate effects of psilocybin on short-term (1 week) persisting effects and post-session drinking behavior, 4) to evaluate the explanatory value of changes in alcohol craving, self-efficacy, motivation, and other psychological domains in accounting for the observed experimental effect of psilocybin relative to diphenhydramine control and 5) to evaluate pre-post changes in drinking in participants after they receive psilocybin in the third session.

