#### 3.3.12.5.2 Method

Statistical procedures described for Aim 3 will be used to determine if the proposed mediators account for the effectiveness of the psilocybin administration. Changes in proposed primary and secondary mediators will be assessed at weeks 5 and 9 (1 week following drug administration) and drinking outcome (PHDD) will be assessed at weeks 8 and 12 (4 weeks post drug administration). No protection for inflated Type I error will be applied to the testing of the three primary mediators, i.e., Penn Alcohol Craving Scale, and Abstinence Self-efficacy from the AASE, and Readiness from the Readiness Rulers. Performance site and the site by treatment group interaction terms will not be entered into the model.

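### Hypothesis 3 is a three-step sequence, but the protocol tests it only in pieces, and it estimates the second link without session experience in the drinking model

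*Combined protocol and SAP*

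**What the plan says.** Section 2 states Hypothesis 3 in two linked parts. The first says that a more intense session goes with larger shifts in the three 1-week measures (craving, self-efficacy, motivation). The second builds on it: "these changes will in turn predict changes in drinking behavior during the 32 weeks following initial drug administration". Section 3.1.8.1 describes the same causal order as the proposed route to a therapeutic effect. Aim 3 itself is framed a little differently: characteristics of the session are to "mediate effects of psilocybin on short-term (1 week) persisting effects and post-session drinking behavior" (section 1).

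Section 3.3.12.4.1 says that three dimensions of the 5D-ASC and the "total score from the MEQ will be used as independent measures of acute drug effects". Their place in the model is not given. Section 3.3.12.4.2 states: "Tests of statistical mediation will use a product-of-coefficients approach with a bootstrapping procedure". The hierarchical model supplies the a and b "parameter estimates for the between-group contrast (treatment assignment psilocybin versus control", with 1 df. The only other term named is the baseline value of the dependent variable.

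For Aim 4, section 3.3.12.5.2 says: "Statistical procedures described for Aim 3 will be used to determine if the proposed mediators account for the effectiveness" of psilocybin. The mediators there are craving, self-efficacy and readiness at weeks 5 and 9, and the outcome is PHDD at weeks 8 and 12. Section 3.3.12 refers to a separate SAP for the full description of the analyses.

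**The concern.** Hypothesis 3 needs three coefficients in sequence: treatment to experience, experience to 1-week change, and 1-week change to drinking. The method supplies two at a time. The piece that carries the second link, in Aim 4, regresses drinking on treatment and the 1-week change and leaves out the session experience. Experience comes before both and is measured. If it moves both, the coefficient of the 1-week change on drinking picks up the effect of experience.

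At stake is the mechanism conclusion, not the primary efficacy test. Craving or self-efficacy could be reported as the route by which psilocybin works when it is only another consequence of a strong session. Mechanism is the subject of two of the five aims, and section 3.2 presents it as a novel contribution.

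**Working it through.** **1. What the planned models estimate.** T is treatment, E session experience, C 1-week change and Y drinking.

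| Planned product | Source | Link of Hypothesis 3 in its b path |
|---|---|---|
| T → E → C | Aim 3, 1-week effects as outcome | First link, E to C |
| T → E → Y | Aim 3, drinking as outcome | None; C is absent |
| T → C → Y | Aim 4 | Second link, C to Y, without E, at weeks 8 and 12 |

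No row is T → E → C → Y, and no drinking model contains both E and C.

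**2. The pilot figures (Figure 3d, n = 9, all on psilocybin).** The printed p-values reproduce with t = r√(7/(1−r²)). For change in craving against change in PHDD, .726 × √(7/(1−.726²)) = 2.79, p = .027, as printed.

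The partial correlation given E is (r_CY − r_EC·r_EY)/√((1−r_EC²)(1−r_EY²)).

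- Craving, given MEQ: (.726 − (−.810)(−.823))/√((1−.810²)(1−.823²)) = .059/.333 = .18 (95% CI −.60 to .78).
- Craving, given HRS intensity and HRS item 98: .27 and .32.
- Self-efficacy, given MEQ: (−.494 − (.762)(−.823))/√((1−.762²)(1−.823²)) = .133/.368 = +.36 (95% CI −.46 to .85).
- Self-efficacy, given HRS intensity and HRS item 98: +.19 and +.18.

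Craving-PHDD therefore falls from .73 to between .18 and .32, and self-efficacy-PHDD moves from −.49 to between +.18 and +.36. With nine people these values are illustrative only.

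**3. How large the misattribution can be.** N = 171 comes from section 3.3.12.7 (180 less 5%). The rest is assumed, because the plan gives no values:

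- Treatment raises E by 1 or 2 SD. E has SD 1 on psilocybin and 0.3 or 1 on control.
- C = rE + √(1−r²)·noise, and Y = rE + √(1−r²)·independent noise. C has no effect on Y. (r is the within-arm correlation where E has SD 1.)

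With v the average within-arm variance of E, v = (1 + 0.3²)/2 = .545 or (1 + 1²)/2 = 1, the Aim 4 model estimates

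b = r²v/(r²v + 1 − r²)

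although the true value is 0. At r = .5, b = .136/.886 = .15 (v = .545) or .25 (v = 1). At r = .8, b = .349/.709 = .49 or .64. In this set-up b is also the share of the treatment effect wrongly assigned to C, because a and the total effect are both r times the shift in E.

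Share of simulated trials that declare C a mediator (two-sided 5%, all coefficients in the product significant):

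| r | Two-step product (Aim 4) | Serial product, E in the drinking equation |
|---|---|---|
| .2 | 2-5% | 2-7% at every r |
| .3 | 5-21% | |
| .5 | 49-92% | |
| .8 | 100% | |

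A separate run of 2,000 trials per setting gave 2-6%, 5-23%, 47-91% and 100%, with 3-6% for the serial product. A 500-draw percentile bootstrap (400 trials; 2 SD shift, control SD 0.3) gave 4.5%, 9.8%, 52.5% and 100%, with 3-8% for the serial product.

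**The case against.** The strongest reply is that both predictions in Hypothesis 3 have a planned estimate. The wording is predictive, Aim 3 names experience as a mediator of two separate outcomes, and a two-step product suits that. Calling the experience scores independent measures leaves their role open. On this view the text is under-specified rather than wrong. Part of this stands, and it limits the point.

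- A reader might infer that the hypothesis is not tested at all, or that no model holds experience and the 1-week change together. The documents do not support that. The Aim 3 model with 1-week effects as outcome contains both and estimates the first link. What is missing is the joint chain and the second link adjusted for experience.
- A reader might take the pilot as showing that craving has no role, or that self-efficacy works in reverse. It shows neither. The intervals are very wide, and the unadjusted self-efficacy correlation was not significant (p = .177).
- A reader might conclude that the trial will report a false mechanism. That depends on correlations the trial has not assumed. At .2 the problem is negligible. At .3 it is small to moderate.
- The SAP may already contain a serial model. Its text was not in the material reviewed, so the point applies to the protocol text.

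Under-specification does not remove the concern about Aim 4. Its procedure ties a and b to treatment and names no adjustment for experience, so following the text as written leaves experience out.

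**Conclusion.** The point holds in a limited form. The protocol tests Hypothesis 3 only piecewise. The second link is estimated without session experience and only at weeks 8 and 12, although the hypothesis covers 32 weeks. If experience drives both the 1-week change and drinking, with within-arm correlations of .5 or more, the Aim 4 product would credit a mediator with no effect in roughly half to all trials, while a serial test stays near its nominal level. The pilot correlations of MEQ with these changes are .76 to .88 in size, which is reason enough to adjust, but n = 9 cannot fix the size in this trial. The rates rest on linear relations, a 1-2 SD treatment effect on experience and a control-arm SD of 0.3-1. The primary analysis is unaffected.

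**What to change.** 1. Check the SAP for a serial model. For every test under Aims 3 and 4, state the cause, the mediator or mediators, and the outcome.
2. For Hypothesis 3, add the serial product: treatment, first-session experience, week-5 change (craving, self-efficacy and readiness in turn), then PHDD after the week-5 visit. Keep treatment and experience in the drinking equation and bootstrap by participant. The daily Time-line Follow-back allows drinking before the week-5 visit to be left out.
3. Use the experience measures already listed in section 3.3.12.4.1: the three 5D-ASC dimensions and the MEQ total. Section 3.3.12.2.1 names the 5D-ASC as the primary measure of hallucinogen effect, so MEQ should not stand alone.
4. Run it first on PHDD to week 8, before second-session dosing, and then over the rest of the 32-week window. State with the later result that the first-session MEQ score also enters the second-session dose decision (section 3.3.8.1.3), so its path to later drinking may run partly through dose.
5. Report the Aim 4 product beside it and describe it as unadjusted for experience.

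The cost is extra modelling on data already scheduled in Table 1. Four experience measures and three mediators give 4 × 3 = 12 products per window, so the plan should say in advance how they will be read. Intervals for the second link will be wider. If the chain is true (2,000 simulated trials per setting, N = 171, control-arm SD 0.3, experience-craving correlation .3 to .5), power is about 58-62% for a craving-to-drinking slope of .2, and 80-91% for .3. The result stays model-based, because neither experience nor the 1-week change is randomised.

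### The Aim 4 drinking model leaves out the pre-session value of the mediator, so the mediator-to-drinking coefficient can be biased

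*Combined protocol and SAP*

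**What the plan says.** Section 3.3.12.4.2 (Aim 3 method) sets the approach: "Tests of statistical mediation will use a product-of-coefficients approach with a bootstrapping procedure". It fits the *a* path (treatment to mediator) and the *b* path (mediator to drinking) by hierarchical linear models. The covariate rule is "baseline values of the dependent variable will be entered in level 2".

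Section 3.3.12.5.2 carries this over to Aim 4: "Statistical procedures described for Aim 3 will be used to determine if the proposed mediators account for the effectiveness of the psilocybin administration". On the mediators it says: "Changes in proposed primary and secondary mediators will be assessed at weeks 5 and 9". PHDD is taken at weeks 8 and 12. The only further statement on model terms is an exclusion: "Performance site and the site by treatment group interaction terms will not be entered into the model". No reference visit is named for the changes.

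Hypotheses 3 and 4 (section 2) are worded as changes in craving, self-efficacy and motivation. Sections 3.3.12.4.1 and 3.3.12.5.1 name the measures as scores (Penn craving total, abstinence confidence, readiness). Table 1 (3.3.10) schedules all three scales at baseline and at weeks 4, 5, 8 and 9.

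**The concern.** The rule works differently in the two halves of the mediation analysis. In the *a*-path model the dependent variable is the mediator, so the mediator's own baseline is entered. In the *b*-path model the dependent variable is drinking, so baseline drinking is entered and nothing accounts for where the participant's craving, self-efficacy or readiness stood before the session.

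A change score is negatively related to its own starting value. Regressing drinking on change alone forces the pre- and post-session scores to have equal and opposite coefficients. Regressing on the post-session level alone forces the pre-session coefficient to zero. If neither restriction is true, the *b* coefficient absorbs the misfit, and so does the product *a* × *b* on which Hypothesis 4 and the mediator-to-drinking link of Hypothesis 3 rest. Error in the indirect effect also passes into the direct effect.

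**Working it through.** **Inputs from the documents.** Covariate rule and product method: 3.3.12.4.2. Changes at weeks 5 and 9: 3.3.12.5.2. Analysed sample: 180 × 0.95 = 171 (3.3.12.7). The plan gives no power or effect size for mediation, so there is no planned figure to reproduce. Its only power statement concerns Aim 2 and is not used here.

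**Assumed, because not given.** Pre- and post-session mediator SDs, their correlation *r*, the correlation of baseline drinking with the mediator, and the true coefficients.

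**Set-up.** Let M4 and M5 be the mediator before and after session 1, D = M5 − M4, Y0 baseline drinking, and Y = b·M5 + d·M4 + g·Y0 + treatment + error.

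**Mediator as change, M4 omitted.** With unit SDs and Y0 unrelated to the mediator:

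- cov(D, M5) = 1 − r; cov(D, M4) = −(1 − r); var(D) = 2(1 − r).
- Coefficient on D = [b(1 − r) − d(1 − r)] / [2(1 − r)] = (b − d)/2.

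So d = 0 (drinking follows the post-session level) retains 0.50 of b for any r; d = 0.5b retains 0.25; d = b retains 0; d = −b (drinking follows change itself) retains 1.00.

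With post/pre SD ratio k and d = 0, the retained share is (k² − rk)/(k² + 1 − 2rk):

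- k = 0.8: r = 0.3 gives 0.40/1.16 = 0.345; r = 0.7 gives 0.08/0.52 = 0.154.
- k = 1.25: r = 0.3 gives 1.1875/1.8125 = 0.655; r = 0.7 gives 0.6875/0.8125 = 0.846.

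If baseline drinking correlates 0.3 to 0.6 with M4, and with M5 only through M4, the retained share is 0.53 to 0.66 (k = 1, d = 0). If it correlates equally with M4 and M5, the share stays at 0.50.

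**Mediator as level, M4 omitted.** The coefficient on M5 is b + d·r. With d = 0 there is no bias. With b = 0, d = 0.3 and r = 0.6 it is 0.18 although the true value is zero.

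**M4 included.** Since M5 = D + M4, the change and level forms give the same b, and the estimate is unbiased under this set-up.

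**Illustrative simulation (all effects assumed).** N = 171, r = 0.6, equal SDs, b = 0.30, a = −0.40, direct effect −0.20, 4,000 runs. Power is for joint significance of *a* and *b*, not the planned bootstrap.

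| Y0–M4 correlation | d | b, change only | b, with M4 | Power, change only | Power, with M4 |
|---|---|---|---|---|---|
| 0 | 0 | 0.152 | 0.302 | 41% | 84% |
| 0.4 | 0 | 0.169 | 0.299 | 49% | 83% |
| 0.4 | 0.15 | 0.104 | 0.299 | 20% | 83% |
| 0.4 | −0.30 | 0.299 | 0.299 | 86% | 83% |

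In the first row the indirect effect falls from −0.12 to −0.06 and the direct effect moves from −0.20 to −0.26. The total is unchanged: −0.20 − 0.12 = −0.26 − 0.06 = −0.32.

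**False mediator.** With b = 0, d = 0.3 and Y0 unrelated to the mediator, the change form gives (0 − 0.3)/2 = −0.15, significant in a little over 40% of runs. Its sign is the reverse of d. The level form gives 0.18, significant in about 70% of runs. With M4 entered the rate is about 5%.

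**Session 2.** Week 8 follows randomisation and the first dose. Suppose, for illustration, treatment effects of −0.3 SD at week 8 and −0.5 SD at week 9, with a within-arm slope of 0.6. Adjusting the week 9 mediator model for week 8 gives a = −0.5 − 0.6 × (−0.3) = −0.32. The part carried over from session 1 is removed.

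**The case against.** Five points can be made for the plan.

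- **Drinking may follow change.** Both hypotheses are worded that way, and the pilot correlations in 3.3.3.2 relate change to change. If d = −b, the change model is unbiased and slightly more powerful. This stands, but the plan does not establish that relation, and 3.3.12.4.1 and 3.3.12.5.1 list scores rather than differences.
- **A raw difference is not specified.** The Aim 4 text gives timing and calls the mediators changes; it does not define the regressor. This stands. It shifts the problem from attenuation to possible confounding and does not remove it.
- **The rule sits in the Aim 3 method.** There, the 5D-ASC dimensions and "the total score from the MEQ will be used as independent measures of acute drug effects". These session-experience scores have no pre-session value, so the point does not reach them. The *a* path already receives its baseline. Both limits are accepted.
- **A fuller SAP is cited in 3.3.12.** No mediation text in the document adds the missing covariate. If a separate SAP does, only alignment is needed.
- **These are mechanism aims.** Correct: the Aim 2 analysis is unaffected.

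A reader might infer that the plan halves the mediation effect, or that the test loses most of its power. The documents support neither. Halving needs three conditions together: an effect through the post-session level only, equal SDs, and baseline drinking that does not separate the two mediator scores. The power figures rest on effect sizes that the plan does not give.

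**Conclusion.** The concern holds for the mediator-to-drinking model of Aim 4 and the corresponding link of Hypothesis 3. As written, that model adjusts for baseline drinking and omits the pre-session mediator score. The result is unbiased only in special cases: drinking follows change and change is entered, or the pre-session value has no effect of its own and the level is entered. Otherwise *b* and the indirect effect are biased. Under the change form the retained share runs from about 0 to about 1 across the assumptions tried, with one half as the equal-SD, level-only case. Under the level form a coefficient can appear where none exists. The direction and size in this trial cannot be settled from the documents. The simulated powers show how much could turn on the omission; they do not predict this trial's power.

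**What to change.** In 3.3.12.5.2, and for the mediator-to-drinking link under 3.3.12.4.2:

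- Enter the pre-randomisation value of each mediator (week 4) in the drinking model, alongside baseline PHDD. State that this is the score obtained before dosing, because the week 4 column of Table 1 also holds the acute-effects scales.
- State whether each mediator enters as a change or a level, and the reference visit for each change. If the reference visit is the same as the covariate visit (week 4), the two forms give the same coefficient.
- For the week 9 mediator, keep the pre-randomisation value as the covariate. Do not adjust the mediator model for week 8, since that removes carried-over session 1 effect.
- State that this does not apply to the 5D-ASC and MEQ mediators.

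The cost is wording and one covariate that is already collected. If drinking follows change itself, power falls slightly (86% to 83% in the illustration).
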